**Table 1. Assessments**

	Screening	Day 0 - First Infusion (Ketamine or Saline) and Day 0+28- Second Infusion (Ketamine or Saline)					Day 1 and Day 1+28	Day 2 and Day 2+28	Day 3 and Day 3+28	Day 5 and Day 5+28	Day 7 and Day 7+28	Day 10 and Day 10+28	Day 14 and Day 14+28
		-1 hour	0 hour	1 hour	2 hour	3 hour							
INTERVENTION													
Infusion			X										
BAT													
Impromptu Speech*		X					X				X		

MEDICAL ASSESSMENT												
Vital Signs												
Vital Signs	X	X	X	X	X	X						
Physical Exam	X	X				X						
EKG	X	X				X						
Blood Tests	X											
Urine Tests	X	X										
CLINICAL RATINGS												
SCID	X											
LSAS	X	X			X	X	X	X	X	X	X	X
SDS	X	X			X	X	X	X	X	X	X	X
VAS**	X	X	X	X	X	X	X	X	X	X	X	X
ASI		X										
SSPS**		X				X				X		
PANAS**		X				X				X		
BAI**	X	X			X	X	X	X	X	X	X	X
HAM-D	X	X			X	X	X	X	X	X	X	X
STAI**	X	X			X	X				X		X
CGI	X	X			X	X				X		X
OE		X										
TE					X	X				X		
MMSE	X	X	X	X	X	X						
BPRS-PS	X	X	X	X	X	X						
CADSS	X	X	X	X	X	X						

\*All ratings and tests are assessed before the impromptu speech on the behavioral assessment test (BAT) days

\*\*These ratings are assessed both before and after the impromptu speech on the behavioral assessment test (BAT) days

Table 1 presents the overall design of this study in terms of interventions, clinical ratings, behavioral assessments and laboratory examinations. A baseline screening assessment to determine study eligibility, clinical ratings, and physical health will be conducted at least one week prior to study enrollment. On the first study day, the patients will receive an infusion of ketamine or placebo, and the second infusion will be performed on day 28. A battery of clinical and cognitive rating scales will be employed to determine the effects of ketamine administration on mood, anxiety, perceptual distortions, and cognitive function for the first 3 hours and first 14 days following the placebo and ketamine infusion period. Twenty-eight days will separate the first and second infusions.

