**Intervention**

**Ketamine Administration:** Following an overnight fast, ketamine 0.5 mg/kg (or saline) will be administered over a 40 minute period. Ketamine administration will be performed on the Clinical Neuroscience Research Unit. A research nurse and physician will be present at all times during the procedure. Ketamine has been studied in over 10,000 patients in more than 100 separate studies. Ketamine has a wide therapeutic window, and is usually given in doses of 1mg/kg – 4.5mg/kg IV over 60 seconds when used as a sole anesthetic agent. Ketamine side effects include elevated blood pressure and disorientation, among others. Our institution has had experience using ketamine safely in research studies involving psychiatric patients for the last 15 years.

The most common side effects of ketamine are (1) Elevated blood pressure, breathing rate and pulse rate, (2) Local pain at injection site and temporary rash and (3) A variety of temporary psychological symptoms including, but not limited to anxiety, sadness, disorientation, insomnia, flashbacks, hallucinations, and psychotic-like symptoms. These types of reactions have occurred in approximately 12% of patients given higher doses of ketamine when used for anesthesia. These symptoms usually last no more than a few hours. The most serious possible side effects of ketamine use are (1) Substance abuse/dependence, (2) Elevations in intraocular pressure that could lead to vision problems, (3) Allergic reaction and (4) Elevation in blood pressure that could result in stroke, heart problems and death. All the serious possible side effects of ketamine are rare. As a precaution all patients will be administered ketamine and monitored at the Clinical Neuroscience Research Unit for 3 hours following ketamine infusions. If the side-effects do not dissipate we will additionally offer patients hospitalization at Connecticut Mental Health Center for psychiatric side-effects or YNHH for medical side-effects.

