**Assessments**

The rating scales utilized in the trial are detailed in the table below. Ratings 1-14 days post infusion will be conducted by raters that are blinded to treatment assignment and will not be present or have access to the data collected on the initial infusion day. All rating scales documenting the psychotomimetic side effects of ketamine (BPRS and CADSS) will be performed by a separate rater who is blinded to treatment assignment but was present at the initial infusion. All ratings and assessments will be performed by trained research staff.

The SCID (Structured Clinical Interview for DSM disorders) on the screening day may take up to 2 hours with complex patients. All other assessments combined will likely take less than 3 hours on assessment days. Of note, “Day 0” will likely require a full 8-hour day because patients receive the infusion and receive assessments before and after the infusion. On Day 0, food after the infusion will be provided at CMHC.

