term toxicity associated with ketamine administration. However the acute behavioral side effects of this medication warrant particular attention. Krystal et al, administered ketamine to healthy subjects at the West Haven VAMC(Krystal, Karper et al. 1994). The study showed that ketamine produces dose-related effects at sub-anesthetic effects in healthy subjects. At 0.1 mg/kg administered over 40 minutes, the low dose in the VA protocol, ketamine produced little more than a tingling in the extremities and a "little buzzing in the head". At 0.5 mg/kg, the VA study's high dose, and the dose proposed in this protocol, ketamine transiently elicited both the positive and negative symptoms of schizophrenia, dissociative symptoms, attentional impairments, a preferential impairment in delayed over immediate recall, increased perseverative errors on the Wisconsin card sort test, and decreased verbal fluency. In the sub-anesthetic dose utilized in this study, perceptual changes dissipate within 10-20 minutes following the termination of ketamine infusion. Ketamine also increased prolactin and cortisol, while blunting a test day decline in plasma HVA. Ketamine increased systolic and diastolic blood pressure by approximately 10-15 mm Hg, without a clear effect on pulse. Ketamine did not produce gross disorientation, as evidenced by complete absence of an effect on the MMSE and the successful completion of all categories on the Wisconsin card sort test. There have been no medical complications of ketamine administration to date. Out of the 18 subjects administered ketamine 0.5 mg/kg over 40 minutes, 8 complained of blurred vision and two subjects vomited. Both the individuals who vomited were noted to have horizontal nystagmus. There have not been adverse psychological reactions in any of the healthy subjects. There is no doubt that ketamine has clear and, in some cases, dramatic effects upon cognitive function. Some people find these effects pleasant or interesting and others find these effects frightening. In prior studies, all subjects have been thoroughly prepared for possible ketamine response prior to testing and debriefed at the end of each test day. As a result, only two subjects terminated their participation in either study prematurely. No subject has had adverse or lingering responses to ketamine following a test day. Also, none of the subjects experienced "flashbacks" to their ketamine experiences following a test day. These findings are very consistent with the earlier work of Domino and his colleagues. Thus, ketamine appears to be safe and, despite the intensity of its short-term behavioral effects, well tolerated. The extent to which the effects of ketamine are perceived as unpleasant is context dependent and can be reduced by preparing individuals in advance for the possible responses to ketamine. The response to ketamine appears to be reduced by a number of medications, including benzodiazepines and antipsychotic agents.

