
Since 1989, Yale researchers have administered ketamine to over 140 healthy subjects, 30 recovering alcohol patients and 20 patients with major depression. Adverse effects in response to ketamine infusion have been **mild and transient**, with no evidence of any clinically significant adverse side effects. We have reported 8 adverse events associated with ketamine administration to the Institutional Review Boards of Yale and/or the West Haven VA since October of 2000. None was considered serious and all resolved shortly after discontinuation of the ketamine infusion or within two weeks of the ketamine test day. Adverse events included nausea and vomiting, sedation, hypotension, insomnia and nightmares, headaches, visual and somatosensory perceptual alterations, strong paranoid feelings, and anxiety.

None of the patients or healthy subjects studied to date has had any *long-term* adverse consequences as a result of ketamine administration. This impression is supported by follow-up data up to 2 years on 132 healthy subjects participating in ketamine studies at Yale

University and at Washington University at St. Louis (unpublished data). We examined follow-up assessments collected in a sub-sample of 132 healthy subjects who returned for subsequent testing over a duration of 1 week to 2 years. These subjects completed a similar battery of assessments when they reappeared as they completed in their earlier testing. In this analysis, no significant changes occurred in any measure between their initial and follow-up assessment.

In a previous study where ketamine was administered to depressed subjects there were adverse effects, though none were severe and none persisted beyond 110 minutes. Conversely, there was a significant transient improvement of depressive symptoms.

**Blood drawing/intravenous placement:** Bruising or thrombosis can occur with placement of the intravenous line. A total of 30cc will be drawn at baseline to ensure subject health before entering the study. The risks of blood draws include brief pain at the time of needle insertion, bruising, swelling at needle site and rarely, fainting or infection. The amount drawn is considerably less than 500 cc, the amount approved by the Red Cross.

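### With 0 hour undefined and ratings only on the hour, the CADSS and BPRS-PS probably miss the peak perceptual and dissociative effect of a 40-minute infusion

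*Combined protocol and SAP*

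**What the plan says.** The Intervention paragraph of the Research Plan (Section V, item 3) states that "ketamine 0.5 mg/kg (or saline) will be administered over a 40 minute period".

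Table 1 groups both infusion days under one header, "Day 0 - First Infusion (Ketamine or Saline) and Day 0+28- Second Infusion (Ketamine or Saline"), with columns at -1, 0, 1, 2 and 3 hours. The infusion is marked under 0 hour. The CADSS and BPRS-PS rows have marks at screening and in the on-the-hour infusion-day columns. No column lies between 0 and 1 hour, and nothing in the text schedules either scale during the infusion or at its end.

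The text under Table 1 gives the purpose of the battery: "to determine the effects of ketamine administration on mood, anxiety, perceptual distortions, and cognitive function for the first 3 hours" and for the following 14 days. The Assessments paragraph gives these two scales a specific job: "All rating scales documenting the psychotomimetic side effects of ketamine (BPRS and CADSS) will be performed by a separate rater", someone who is blinded but attended the infusion.

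On time course, the Risks section (Section V, item 9, Ketamine administration) says that at the dose used here "perceptual changes dissipate within 10-20 minutes following the termination of ketamine infusion". The same section reports, from an earlier study in healthy subjects, a "complete absence of an effect on the MMSE". Of adverse effects in an earlier study of depressed subjects, it says that "none were severe and none persisted beyond 110 minutes".

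**The concern.** The two scales exist to record a short-lived effect, and the protocol says roughly when that effect ends. Set against the rating grid, that time leaves a gap of an hour after 0 hour in which nothing is rated, and on the natural reading the whole perceptual effect falls inside the gap.

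Two uses of the data are at stake. The first is the description of acute psychotomimetic effects. Low scores from minute 60 onward could be read as good tolerability when they reflect only when the question was asked. The second is the assessment of blinding. The Overview accepts that ketamine's side effects frequently reveal the assignment, and the Treatment Evaluation (TE) item asks participants which infusion they think they had. Without a rating taken while the effect is present, those guesses cannot be set against the size of the acute experience.

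**Working it through.** **Inputs**
- Infusion length: 40 min (Intervention).
- Perceptual clearing: 10 to 20 min after the end of infusion (Risks).
- Rating times: 0, 60, 120 and 180 min relative to 0 hour (Table 1 columns).
- Position of 0 hour relative to the infusion: not stated, so three readings are tried.

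**Formula.** Clearing time = start of infusion + 40 + (10 to 20) min. If 0 hour is the start, this is 0 + 40 + 10 = 50 to 0 + 40 + 20 = 60 min.

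| Reading of 0 hour | Clearing (min from 0 hour) | 0-hour rating | 1-hour rating | 2-hour rating | 3-hour rating |
|---|---|---|---|---|---|
| Start of infusion | 50 to 60 | before any effect | 0 to 10 min after clearing | 60 to 70 min after | 120 to 130 min after |
| Middle of infusion | 30 to 40 | during infusion | 20 to 30 min after | 80 to 90 min after | 140 to 150 min after |
| End of infusion | 10 to 20 | 10 to 20 min before clearing | 40 to 50 min after | 100 to 110 min after | 160 to 170 min after |

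On the start reading, no rating falls clearly inside the window. The 1-hour rating, 60 - 40 = 20 min after the infusion ends, can catch only its last moment. On the other two readings the 0-hour rating does catch the effect.

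**Which reading fits better.** If 0 hour were the end of infusion, the -1 hour column would fall 60 - 40 = 20 min before the infusion starts. That column holds the physical exam, EKG, urine tests, most of the scales and a speech task of up to 10 minutes, with several scales repeated after it. Twenty minutes is too short for this. Table 1 also marks the infusion itself at 0 hour. The start reading is the more natural one, though no sentence confirms it.

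**Longer-lasting effects.** The time origin of the 110-minute limit is not given. Counted from the start of infusion, it runs past the 60-minute rating but not the 120-minute one. Counted from the end, it reaches 40 + 110 = 150 min, past the 120-minute rating too. Some adverse effects could therefore still be present at 1 hour, and perhaps at 2 hours.

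**State of the table.** In the text copy of Table 1 the header has 13 columns, but the rating rows carry 12 cells, so one infusion-day cell per row was lost in conversion. The sixth CADSS and BPRS-PS mark could be 3 hour or Day 1. Every possible infusion-day column is still on the hour, so the timing result does not depend on which cell was lost.

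**The case against.** The strongest reply is that 0 hour is undefined. A separate -1 hour column already supplies a pre-drug rating, so the 0-hour rating may be meant for the infusion or its end. The stated aim of covering the hours after the infusion period, and the 3-hour observation after it, leave room for that. If so, the peak is captured. This stands as a limit on certainty. It does not remove the need for a change, because staff cannot tell from the protocol whether that rating is pre-drug or at peak.

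The clearing figure covers perceptual changes only, and minute 60 is the edge of its range. Other adverse effects may last up to 110 minutes, so some patients may still score above baseline at 1 hour. That also stands. It is why the conclusion is that the peak is probably missed, not that nothing would be recorded.

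The plan also has other safeguards: bedside staff, continuous monitoring during the infusion, separate raters and the TE item. Statistical Considerations plans no CADSS or BPRS-PS analysis. These points limit the consequences, but none of them measures the size of the acute effect.

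A reader might infer that the MMSE misses an acute effect as well. The documents do not support this: the Risks section reports no MMSE effect in the earlier healthy-subject study that used this dose. A reader might also infer that efficacy is compromised. It is not, because the primary analysis uses VAS improvement over the 3 days after infusion.

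**Conclusion.** The point holds for the CADSS and BPRS-PS. As written, the schedule does not assure a rating of either scale during the peak. On the natural reading, the first rating after the start comes 0 to 10 minutes after perceptual changes have cleared. Scores from it would probably understate the effect and could not usefully be related to treatment guesses.

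This rests on two assumptions: that 0 hour is the start of infusion, and that the dissociative and positive symptoms these scales rate follow a time course similar to the perceptual changes. The protocol calls those symptoms transient at this dose but gives them no clearing time of their own.

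The amount of understatement cannot be calculated from the documents, and a claim that scores would certainly be at baseline goes further than they allow. The damage is confined to describing side effects and assessing unblinding.

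**What to change.** - In Table 1, define 0 hour as the start of infusion.
- Retime the 0-hour CADSS and BPRS-PS to the end of infusion, about 40 minutes after the start, at both infusions, and label that time in the table.
- Keep -1 hour as the baseline for these two scales, and 1, 2 and 3 hours as recovery points.
- Report the change from -1 hour to the end of infusion as the acute-effect measure, separate from efficacy, and set it beside the TE guesses.
- Leave the VAS and MMSE timings unchanged. The VAS is the primary instrument. Its -1 hour rating is taken before and after the speech task, so the 0-hour VAS may be the only infusion-day pre-drug value not tied to that task, and the plan does not name the baseline used for improvement.

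The cost is small. The number of ratings stays the same, and the side-effect rater is already at the infusion. The repeat pre-infusion CADSS and BPRS-PS baseline is lost, and some patients may find the scales harder to complete at that moment. If the full table turns out to have no 0-hour mark for these scales, the change would instead add one rating of each scale per infusion.

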The results of several clinical studies suggest that ketamine may also have significant anxiolytic effects. Patients with major depressive disorder given a single ketamine infusion have shown strong and significant reductions in comorbid anxiety symptoms. A trial including 11 depressed patients demonstrated a significant reduction in anxiety symptoms (Hamilton Anxiety Rating Scale (HAM-A)) following ketamine infusion (mean HAM-A pretreatment score  $23.4 \pm 6.5$ ; mean HAM-A score after 230 minutes  $14.3 \pm 7.8$ ;  $t(9) = 3.39$ ,  $p < .01$ , Effect Size=1.4)(Salvadore, Cornwell et al. 2009). This improvement is supported by one of the earlier placebo-controlled trials of ketamine which demonstrated that the psychic anxiety item was one of 4 (out of 21) items on the HAM-D demonstrating significant improvement after ketamine infusion (Hofmann, Newman et al. 1995, Zarate, Singh et al. 2006). We propose a randomized, placebo-controlled crossover study to explore the efficacy and time course of action of intravenous ketamine in the treatment of SAD.

3. **Research Plan:** Summarize the study design and research procedures using non-technical language that can be readily understood by someone outside the discipline. Be sure to distinguish between standard of care vs. research procedures when applicable, and include any flowcharts of visits specifying their individual times and lengths. Describe the setting in which the research will take place.

- We propose a crossover trial in which 18 adults with severe SAD will be given a single infusion of ketamine or saline (placebo) and their SAD symptoms will be followed over a two week period.
- We will require at least a 4-week interval between infusions in order to minimize carryover effects.
- An 18 subject crossover trial will give us sufficient power to demonstrate a significant effect of ketamine (compared to placebo) if the symptom improvement is comparable to that observed in Major Depressive Disorder.

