**Psychiatric evaluation, rating scales and questionnaires:** These are all non-invasive, should add no risk, and have been used without difficulty or adverse events in previous studies with a similar population. The major disadvantage is the time taken to complete them.

**Clinical Deterioration:** There is a risk that a participant may experience an increase in SAD or depressive symptoms due to the natural course of the illness or poor response to ketamine administration. Because subjects will be asked to refrain from changing any psychotropic medication over the course of the study, clinical progress will be monitored closely with frequent HAM-A and HDRS ratings and frequent contact with clinic personnel. The following are criteria for evaluation and possible pharmacological and/or non-pharmacological treatments: (1) An increase of 25% in HAM-A score at any time over the course of treatment (lasting beyond acute administration studies), (2) new-onset of suicidal ideation or an increase in passive suicidal ideation.

**10. Minimizing Risks:** Describe the manner in which the above-mentioned risks will be minimized.

**Protection of subjects:** Effective screening should exclude individuals who will be placed at greater risk in this study because of medical conditions or psychiatric symptomatology. A detailed medical and psychiatric history, physical examination, and laboratory studies must be conducted prior to commencing the study. All the tests will be done in the presence of constant medical supervision with experienced nursing and technical staff.

**Ketamine Administration:** The most common side effects of ketamine are (1) Elevated blood pressure, breathing rate and pulse rate, (2) Local pain at injection site and temporary rash and (3) A variety of temporary psychological symptoms including, but not limited to anxiety, sadness, disorientation, insomnia, flashbacks, hallucinations, and psychotic-like symptoms. These types of reactions have occurred in approximately 12% of patients given higher doses of ketamine when used for anesthesia. These symptoms usually last no more than a few hours. The most serious possible side effects of

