Health Center Investigational Drug Service phone number, and regular hours telephone numbers of their study physician and research support staff ([name] [contact]), should unpleasant effects occur after the subject has left the testing facility. All participants are contacted 1, 2, 3, 5, 7, 10, 14, 21, and 28 days after each infusion for safety reasons. In addition, participants will be contacted 1, 2, 3, 5, 7, 10, and 14 days after each infusion to administer symptom ratings. Participants will be instructed and encouraged to contact the treatment team between scheduled meetings should their distress worsen.

In order to enroll in the study, patients must not have a lifetime history of substance abuse or dependence, thereby reducing the risk of ketamine substance abuse/dependence by study participants.

**Blood drawing/intravenous placement:** The risks of blood draws and intravenous line placements are rare, and when these are done under sterile conditions by trained personnel the occurrence is even more remote.

**Psychiatric evaluation, rating scales, questionnaires, speech tasks, and attention bias tasks:** In order to minimize risks associated with the psychiatric ratings and ensure the accuracy of reporting, these measures will be administered by a trained research nurse and supervised by a study physician. During the impromptu speech, participants have the option to stop the speech at any time if they experience significant distress.

**Clinical deterioration:** If a participant shows significant worsening of symptoms, he or she will be evaluated for clinically appropriate pharmacological and non-pharmacological treatments by a clinic psychiatrist and followed until successful contact with a community provider is made. Patients will be informed that the decision to initiate a course of psychotropic medication will not affect their eligibility to participate in future studies, to receive treatment at the Connecticut Mental Health Center or Yale, or to receive treatment on a private basis from a referring clinician.

**11. Data and Safety Monitoring Plan:** Include an appropriate Data and Safety Monitoring Plan (DSMP) based on the investigator's risk assessment stated below. (Note: the HIC will make the final determination of the risk to subjects.) For more information, see the Instructions, page 24.

- a. What is the investigator's assessment of the overall risk level for subjects participating in this study? This is a moderate risk study.

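### The 25% HAM-A criterion for worsening anxiety has no scheduled score behind it: HAM-A is in neither Table 1 nor the rating-scale list

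*Combined protocol and SAP*

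**What the plan says.** Section V, item 9 (Risks), Clinical Deterioration, notes that patients are asked not to change psychotropic medication during the study. For that reason, it says, "clinical progress will be monitored closely with frequent HAM-A and HDRS ratings and frequent contact with clinic personnel". It then gives two criteria for evaluation and possible treatment. The first is "An increase of 25% in HAM-A score at any time over the course of treatment (lasting beyond acute administration studies"). The second is new suicidal ideation or a rise in passive ideation. Only the first is numeric, and only the first concerns anxiety.

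The schedule is set out elsewhere: "Table 1 presents the overall design of this study in terms of interventions, clinical ratings, behavioral assessments and laboratory examinations". The Assessments text in Section V, item 3 refers the reader to a table for the scales in use, and the numbered Rating Scales list describes 14 instruments. HAM-A is in neither place. Its only other appearance is in item 2 (Background), as a result from an outside depression study: "A trial including 11 depressed patients demonstrated a significant reduction in anxiety symptoms (Hamilton Anxiety Rating Scale (HAM-A)) following ketamine infusion".

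Item 10 (Minimizing Risks) says "participants will be contacted 1, 2, 3, 5, 7, 10, and 14 days after each infusion to administer symptom ratings", without naming scales. It also contains a provision that needs no scale: "If a participant shows significant worsening of symptoms, he or she will be evaluated". Section VI, A.5 repeats that provision as the safeguard for patients on placebo.

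**The concern.** Two parts of the protocol disagree about which scales are collected, and a safety criterion depends on the answer. Table 1 is what a coordinator would use to build case report forms and run visits. If it is followed, the 25% rule has no input.

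This matters because patients give up other options while in the study. Psychotropic medication is held fixed for about two months (Section VI, A.5b) and CBT is not allowed (inclusion criterion 3). The protocol gives the medication restriction as its reason for close rating. If the rule cannot be applied, the decision to evaluate a patient whose anxiety is worsening rests on an undefined judgement of significant worsening.

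**Working it through.** The plan gives no derived figure to reproduce, so the check is a comparison of texts and a count.

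**1. Is HAM-A in the schedule?** The clinical-rating rows of Table 1 are SCID, LSAS, SDS, VAS, ASI, SSPS, PANAS, BAI, HAM-D, STAI, CGI, OE, TE, MMSE, BPRS-PS and CADSS: 16 rows, none of them HAM-A.

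**2. Is it in the scale list?** The list has 14 instruments, none of them HAM-A. All 14 have a row in Table 1, and the table has 16 - 14 = 2 further rows, SCID and MMSE. The list is therefore not complete by itself, so its silence is weaker evidence than the table's.

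**3. Could a damaged table explain the gap?** This is unlikely. HAM-A is absent from two separate places. The other scale promised in the same sentence, HDRS, does have its row, as HAM-D. HAM-D measures depression and cannot supply a HAM-A score.

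**4. How many occasions are affected?** The LSAS, BAI and HAM-D rows each carry 10 marks: screening, pre-infusion, one later time on the infusion day, and 7 follow-up days. The extracted rows have 12 cells under 13 column headings, so the hour of the later infusion-day mark is uncertain, and it is left out. Item 10 confirms the 7 follow-up days (1, 2, 3, 5, 7, 10 and 14).

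- Occasions per patient = 1 screening + 2 infusions x (1 pre-infusion + 7 follow-up) = 1 + 2 x 8 = 17.
- HAM-A scheduled: 0 of 17.
- LSAS, BAI and HAM-D scheduled: 17 of 17 each.

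**5. Who could apply a rule measured from Day 0?** The Assessments text says that the raters on days 1-14 have no access to data from the initial infusion day. The Day 0 pre-infusion score is such data, so these raters could not compute the rise themselves, whichever scale is used.

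**6. Does it touch the efficacy analysis?** No. Item 12 tests average VAS improvement over the first 3 days by paired t-test and defines response on VAS. HAM-A enters neither.

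**The case against.** The strongest reply is that little is lost in practice. Criterion (1) only prompts evaluation and possible treatment, and item 10 and Section VI, A.5 prescribe the same action on significant worsening, with no scale needed. Safety contact is also frequent: "All participants are contacted 1, 2, 3, 5, 7, 10, 14, 21, and 28 days after each infusion for safety reasons". Section X, item 4 adds systematic questions about adverse events and SAD severity. LSAS, BAI and HAM-D would record a deterioration. All of this stands and limits the consequence. It does not repair the rule, because no action threshold is attached to the scales that are collected.

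The count of 17 can also be questioned, since Section X, item 2 pays for 14 assessments and 2 infusion days, 14 + 2 = 16 occasions. Payments need not match ratings, and HAM-A's count is 0 on either total.

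Two stronger readings are tempting. A reader might infer that HAM-A will not be collected, or that patients are unmonitored. The documents do not support that: the Risks paragraph itself commits to HAM-A ratings, so this is a contradiction and not proof of omission, and the other safeguards remain.

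A reader might also infer a second fault of measurable size, because the rule names no reference score and the pre-infusion score before the second infusion could differ from that on Day 0. But a rise over the course of treatment reads most naturally as a rise from the pre-treatment score, and nothing in the text suggests resetting the baseline. The documents give no HAM-A data in SAD, so any figure would rest on assumed changes. The unnamed reference is a missing detail to settle while the rule is being amended.

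**Conclusion.** The concern holds as an internal contradiction in a safety rule. The only numeric criterion for evaluating worsening anxiety uses a scale that the schedule omits at all 17 rating occasions counted here. It should be corrected, because it is cheap to fix and patients are asked to keep treatment unchanged. Its reach is narrow: one numeric prompt for evaluation is unusable if Table 1 is followed. It is not a stopping rule, the scale-free provisions still operate, and the primary analysis and power statement do not depend on it. The conclusion assumes that the HAM-A row was not lost in extraction, which step 3 makes unlikely, and that staff work from Table 1.

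**What to change.** Restate criterion (1) on an anxiety scale already rated at screening, before each infusion and on days 1, 2, 3, 5, 7, 10 and 14. LSAS is simplest: it is already the eligibility measure and has one score per follow-up occasion. BAI would need the pre-speech score to be named, since on speech days "These ratings are assessed both before and after the impromptu speech on the behavioral assessment test (BAT) days".

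The amended rule should state:

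- **Threshold.** A percentage rise, with 25% as the starting proposal. The investigators should confirm it for the new scale, because 25% need not mean the same on LSAS as on HAM-A. For scale, a Day 0 score at the eligibility limit of 60 gives 1.25 x 60 = 75. They should also check that the rise is attainable for the most severe patients, as the documents do not give the LSAS range.
- **Reference.** The Day 0 pre-infusion score (the -1 hour column).
- **Duration.** Keep the requirement that the rise outlasts the acute administration.
- **Who applies it.** A study physician who is not a day 1-14 rater, so that those raters stay shielded from infusion-day data.

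Cost: a wording amendment and agreement on the threshold, with no added visits or ratings.

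Alternatively, keep HAM-A and add it to Table 1 and the Rating Scales list at the same occasions, with the same reference and the same person applying the rule. That costs one more rating per occasion: 17 per patient, or 17 x 18 = 306 if all 18 patients complete.
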